### **HIGHLY EFFECTIVE METHODS OF CONTRACEPTION**

- Male condoms with spermicide
- Hormonal methods of contraception including combined oral contraceptive pills, vaginal ring, injectables, implants, and intrauterine devices (IUDs) such as Mirena® by WOCBP subject or male subject's WOCBP partner.
- Nonhormonal IUDs, such as ParaGard®
- Tubal ligation
- Vasectomy.
- Complete Abstinence\*

\*Complete abstinence is defined as complete avoidance of heterosexual intercourse and is an acceptable form of contraception for all study drugs. Subjects who choose complete abstinence are not required to use a second method of contraception, but female subjects must continue to have pregnancy tests. Acceptable alternate methods of highly effective contraception must be discussed in the event that the subject chooses to forego complete abstinence.

### **3.3.1.2 *Exclusion Criteria***

#### **1. Target Disease Exceptions**

- a) Subjects with suspected brain metastasis are excluded, unless a brain MRI/CT is negative for metastasis

#### **2. Medical History and Concurrent Diseases**

- a) Any history of hepatic encephalopathy
- b) Any prior (within 1 year) or current clinically significant ascites as measured by physical examination and that requires active paracentesis for control
- c) Active coinfection with both hepatitis B and C
- d) Hepatitis D infection in subjects with hepatitis B
- e) Prior malignancy active within the previous 3 years except for locally curable cancers that have been apparently cured, such as basal or squamous cell skin cancer, prostate cancer without evidence of PSA progression or carcinoma in situ such as the following: gastric, prostate, cervix, colon, melanoma, or breast for example.
- f) Subjects with any active autoimmune disease or history of known or suspected autoimmune disease except for subjects with vitiligo, resolved childhood asthma/atopy, type I diabetes mellitus, residual hypothyroidism due to autoimmune condition only requiring hormone replacement, psoriasis not requiring systemic treatment, or conditions not expected to recur in the absence of an external trigger are permitted to enroll.
- g) Uncontrolled or clinically significant cardiac disease
- h) Positive test for human immunodeficiency virus (HIV) or known acquired immunodeficiency syndrome (AIDS)
- i) Known active drug or alcohol abuse
- j) Prior therapy with an anti-PD-1, anti-PD-L1, anti-PD-L2, anti-CD137, or anti-CTLA-4 antibody (or any other antibody or drug specifically targeting T-cell costimulation or checkpoint pathways)
- k) Prior organ allograft or allogeneic bone marrow transplantation
- l) All toxicities attributed to prior anti-cancer therapy other than neuropathy, alopecia and fatigue must have resolved to Grade 1 (NCI CTCAE version 4) or baseline before administration of study drug. Subjects with toxicities attributed to prior anti-cancer therapy which are not expected to resolve and result in long lasting sequelae are permitted to enroll. Neuropathy must have resolved to Grade 2 (NCI CTCAE version 4).
- m) Active bacterial or fungal infections requiring systemic treatment within 7 days
- n) Use of other investigational drugs (drugs not marketed for any indication) within 28 days or at least 5 half-lives (whichever is longer) before study drug administration
- o) Known or underlying medical condition that, in the Investigator's opinion, would make the administration of study drug hazardous to the subjects or obscure the interpretation of toxicity determination or adverse events.
- p) Any history of clinically meaningful variceal bleeding within the last three months

- q) Subjects with a condition requiring systemic treatment with either corticosteroids (> 10 mg daily prednisone equivalents) or other immunosuppressive medications within 14 days of study drug administration. Inhaled or topical steroids and adrenal replacement doses > 10 mg daily prednisone equivalents are permitted in the absence of active autoimmune disease.

### **3. Physical and Laboratory Test Findings**

- a) Laboratory evidence of any underlying medical conditions that, in the Investigator's opinion, will make the administration of study drug hazardous or obscure the interpretation of toxicity determination or adverse events.

### **4. Allergies and Adverse Drug Reaction**

- a) History of severe hypersensitivity reactions to other monoclonal antibodies.
- b) History of allergy to study drug components.

### **5. Sex and Reproductive Status**

- a) WOCBP who are pregnant or breastfeeding
- b) Women with a positive pregnancy test at enrollment or prior to administration of study medication

### **6. Other Exclusion Criteria**

- a) Prisoners or subjects who are involuntarily incarcerated
- b) Subjects who are compulsorily detained for treatment of either a psychiatric or physical (eg infectious disease) illness
- c) Inability to comply with restrictions and prohibited activities/treatments as listed in **Section 3.4**.

#### **3.3.2 1L Nivolumab vs Sorafenib Cohort**

##### **3.3.2.1 Inclusion Criteria**

###### **1. Signed Written Informed Consent**

- a) Subjects must have signed and dated an IRB/IEC approved written informed consent form in accordance with regulatory and institutional guidelines. This must be obtained before the performance of any protocol related procedures that are not part of normal subject care.
- b) Subjects must be willing and able to comply with scheduled visits, treatment schedule, laboratory testing, and other requirements of the study.
- c) Subject Re-enrollment: This study permits the re-enrollment of a subject that has discontinued the study as a pre-treatment failure (ie, subject has not been randomized / has not been treated). If re-enrolled, the subject must be re-consented and inclusion/exclusion criteria reassessed.

###### **2. Target Population**

- a) Subjects with advanced hepatocellular carcinoma
  - i) disease not eligible for surgical and/or locoregional therapies

- ii) progressive disease after surgical and /or locoregional therapies
- b) No prior systemic therapy for hepatocellular carcinoma.
- c) Histologic confirmation of hepatocellular carcinoma.
- i) Subjects with only a radiologic diagnosis of HCC may be enrolled for screening in the study but histological confirmation is mandatory prior to the start of study therapy.
- ii) Evaluable tumor tissue (formalin-fixed, paraffin embedded archival or recent acquisition) must be received by the central vendor (1 block or 15 unstained slides) for correlative studies prior to randomizing a study subject. If archived samples are not available, subjects must consent to a pre-treatment fresh biopsy as a condition of protocol participation. (Note: Fine needle aspiration (FNA) and bone metastases samples are not acceptable for submission).
- d) At least one RECIST 1.1 measurable untreated lesion. All subjects must have at least one previously untreated, unidimensionally measurable lesion by contrast-enhanced spiral computed tomography (CT)  $\geq 10$  mm or contrast enhanced dynamic magnetic resonance imaging (MRI) scan  $\geq 10$  mm (malignant lymph nodes must be  $\geq 15$  mm on short axis) (additional details are included in [Appendix 2](#))
  - i) The lesion can be accurately measured uni-dimensionally according to RECIST 1.1 criteria
  - ii) The lesion has not been previously treated with surgery, radiotherapy, and/or locoregional therapy (eg: radiofrequency ablation [RFA], percutaneous ethanol [PEI] or acetic acid injection [PAI], cryoablation, high-intensity focused ultrasound [HIFU], transarterial chemoembolization [TACE], transarterial embolization [TAI], etc.)
- e) Locoregional therapy for HCC must be completed at least 4 weeks prior to the baseline scan. All acute toxic effects of any prior local treatment must have resolved to National Cancer Institute (NCI) Common Terminology Criteria for Adverse Events (CTCAE) version 4.0 Grade  $\leq 1$ .
- f) Cirrhotic status of Child-Pugh Class A ([Appendix 3](#))
- g) Eastern Cooperative Oncology Group (ECOG) Performance Status of 0 to 1 ([Appendix 4](#))
- h) Subjects are eligible to enroll if they have non-viral-HCC or if they have HBV-, or HCV-HCC, defined as follows:
  - i) Chronic HBV infection as evidenced by detectable HBV surface antigen or HBV DNA. Subjects with chronic HBV infection must be on antiviral therapy and have HBV DNA  $< 100$  IU/mL.
  - ii) Active or resolved HCV infection as evidenced by detectable HCV RNA or antibody.
- i) Screening laboratory values must meet the following criteria, without continuous supportive treatment such as growth factor administration, blood transfusion, coagulation factors and/or platelet transfusion, or albumin transfusion, and should be obtained within 14 days prior to randomization)

- i) Adequate hematologic function:
  - (1) WBC  $\geq 2000/\mu\text{L}$
  - (2) Neutrophils  $\geq 1500/\mu\text{L}$
  - (3) Platelets  $\geq 60 \times 10^3/\mu\text{L}$
  - (4) Hemoglobin  $\geq 8.5 \text{ g/dL}$
- ii) Prothrombin time (PT)-international normalized ratio (INR)  $\leq 2.3$  or Prothrombin time (PT)  $\leq 6$  seconds above control.
- iii) Adequate hepatic function as documented by:
  - (1) serum albumin  $\geq 2.8 \text{ g/dL}$
  - (2) total bilirubin  $\leq 3 \text{ mg/dL}$
  - (3) AST and ALT  $\leq 5$  times the institutional upper limits of normal
- iv) Adequate renal function with a serum creatinine of  $< 1.5 \times \text{ULN}$  or a creatinine clearance  $> 50 \text{ mL/min}$  (Cockcroft-Gault formula)
- j) Adequate cardiac function with a left ventricular ejection fraction (LVEF)  $> 50\%$  as measured by 2-D echocardiography.

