**Table 2: Observed ORR with Exact 95% CI and 90% Lower Bound**

Observed ORR	Exact 95% CI	90% Lower Bound
20%	(9.1%, 35.7%)	12.0%
25%	(12.7%, 41.2%)	16.2%
30%	(16.6%, 46.5%)	20.5%
35%	(20.6%, 51.7%)	24.9%
40%	(24.9%, 56.7%)	29.4%

**Primary Endpoint**Dose Escalation Phase

- The primary objective is safety and tolerability of nivolumab as evaluated by the following endpoints:
  - Incidence of adverse events (AEs), serious adverse events (SAEs), adverse events leading to discontinuation, and deaths.
  - Incidence of clinical laboratory test abnormalities.

Expansion Phase

- ORR, based on assessments by BICR under RECIST 1.1 criteria, is the primary endpoint. It is defined as the proportion of all treated subjects whose BOR is CR or PR. BOR is the best response designation per subject over the study prior to subsequent anti-cancer therapy. For a BOR of CR or PR, the initial response assessment must have been confirmed by a consecutive assessment no less than 4 weeks (28 days) later.

1L Nivolumab vs Sorafenib Cohort

- ORR, based on Investigator assessments under RECIST 1.1 criteria, is the primary endpoint. It is defined as the proportion of all randomized subjects whose BOR is CR or PR. For a BOR of CR or PR, the initial response assessment must have been confirmed by a consecutive assessment no less than 4 weeks (28 days) later.

Nivolumab plus Ipilimumab Combination Cohort

- The primary objective is safety and tolerability of nivolumab plus ipilimumab as evaluated by the following endpoints:
  - Incidence of adverse events (AEs), serious adverse events (SAEs), adverse events leading to discontinuation, and deaths.
  - Incidence of clinical laboratory test abnormalities.
- ORR, as assessed by Investigator under RECIST 1.1 criteria, is the co-primary endpoint. It is defined as the proportion of all treated subjects whose BOR is CR or PR. For a BOR of CR or PR, the initial response assessment must have been confirmed by a consecutive assessment no less than 4 weeks (28 days) later.

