### **3.3 Study Population**

For entry into the study, the following criteria MUST be met. Eligibility criteria for this study have been carefully considered to ensure the safety of the study subjects and to ensure that the results of the study can be used. It is imperative that subjects fully meet all eligibility criteria. No exceptions will be granted.

For entry into the study, the following criteria MUST be met.

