**Table 5.1-2: Screening Procedural Outline for 1L Nivolumab vs Sorafenib Cohort**

Procedure	Pre-Treatment Visit (Baseline)	Notes
Eligibility Assessments		
Informed Consent	X	Original informed consent in screening for protocol participation. Study allows for re-enrollment of a subject that has discontinued the study as an enrollment failure. If re-enrolled, the subject must be re-consented and assigned a new subject number from IVRS.
Inclusion/Exclusion Criteria	X	Assessed during screening period and (re-enrollment if applicable).
Medical History	X	
Child-Pugh Score	X	Child Pugh A5 or A6 only
Safety Assessments		
Physical examination	X	Within 14 days prior to first dose
Physical Measurements	X	Height and Weight. Within 14 days prior to first dose
ECOG Assessment	X	
Vital Signs	X	Including BP, HR, temperature, respiratory rate. Obtain vital signs at the screening visit and within 72 hours prior to first dose.
Assessment of Signs and Symptoms	X	Within 14 days prior to first dose
Concomitant Medication Collection	X	Within 14 days prior to first dose
12 lead ECG	X	Within 14 days prior to first dose
2D Echocardiogram	X	2-D echocardiogram for valve and LVEF evaluation is to be done at baseline and as clinically indicated.
Laboratory Tests	X	Within 14 days prior to randomization to include CBC w/differential and platelet count, LFTs (ALT, AST, total bilirubin, alkaline phosphatase), Alpha fetoprotein (AFP), BUN or serum urea level, albumin, creatinine, Ca+, Mg++, Na+, K+, Cl-, LDH, amylase, lipase, Glucose, TSH, Free T4, Free T3
Serology for Hep B, Hep C, Hep D	X	HepB surface antigen, HepB surface antibody, Hep B Core antibody, HepB DNA Viral load (PCR) Hep C viral load (PCR) and Hep C Ab, Hep D antibody Testing to be completed at the Central Laboratory. Local laboratory Hep D result can be used to assess subject eligibility if central laboratory

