**Table 5.1-2: Screening Procedural Outline for 1L Nivolumab vs Sorafenib Cohort**

Procedure	Pre-Treatment Visit (Baseline)	Notes
		result not available in time.
Pregnancy test (WOCBP only)	X	Serum or urine pregnancy test (minimum sensitivity 25 IU/L or equivalent units of HCG ) to be done at screening visit and repeated within 24 hours of first dose of study therapy
SNP/HLA Sample	X	
Urinary analysis	X	
Coagulation profile	X	Include International Normalized Ratio (INR). If INR cannot be done by the local laboratory, then Prothrombin Time (PT) may be provided instead.
Efficacy Assessments		
Baseline tumor imaging assessment	X	
 
• CT or MRI of the chest, abdomen and pelvis with IV contrast, including required tri-phasic evaluation of the liver.
 
• MRI is acceptable if CT is contraindicated.
 
• Modality (CT or MRI) used at baseline should be used across all imaging timepoints, if possible.
 
• Bone scan is required if clinically indicated.
 
• MRI brain within 28 days prior to first dose of study therapy for subjects with a history of brain metastasis.
 

Other Assessments		
Tumor tissue sample (biopsy)	X	
A formalin-fixed, paraffin-embedded tumor tissue (FFPET) block (preferred) or a minimum of 15 unstained slides of tumor tissue (archival or recent) for biomarker evaluation will be obtained prior to subject randomization.
 
Central lab must provide IVRS with confirmation of receipt of evaluable tumor tissue prior to subject randomization.
 
The tissue submitted will be assessed for quality with a H & E stain (100 tumor cells) and only those subjects who have meet tissue quality thresholds can be randomized. Subjects whose tissue fails the initial quality assessment can be screen failed and re-enrolled if they consent/agree to a new biopsy.

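### In the 1L cohort the deadline for histological confirmation is the start of therapy, but the primary ORR denominator is fixed earlier, at randomization

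*Combined protocol and SAP*

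**What the plan says.** Section 3.3.2.1 (1L cohort, Target Population) lists as item 2.c "Histologic confirmation of hepatocellular carcinoma". Item 2.c.i adds that "Subjects with only a radiologic diagnosis of HCC may be enrolled for screening in the study", but that "histological confirmation is mandatory prior to the start of study therapy". The next item, 2.c.ii, uses a different milestone: evaluable tissue must reach the central vendor, for correlative studies, before the subject is randomized.

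Table 5.1-2 repeats that requirement: "Central lab must provide IVRS with confirmation of receipt of evaluable tumor tissue prior to subject randomization". It describes the check made on the tissue as an H&E quality assessment with a count of 100 tumor cells. Subjects whose tissue fails may be screen-failed and re-enrolled with a new biopsy.

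On eligibility generally, Section 3.3 says "It is imperative that subjects fully meet all eligibility criteria. No exceptions will be granted". In Table 5.1-2 the entry for the inclusion and exclusion criteria reads "Assessed during screening period and (re-enrollment if applicable". The corresponding row of Table 5.1-1, which covers the Dose Escalation and Expansion Phases, goes further and asks that the criteria be confirmed before randomization. Section 3.1.1 sets the screening window at 28 days counted from first dose.

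The Synopsis defines the 1L primary endpoint, ORR, as follows: "It is defined as the proportion of all randomized subjects whose BOR is CR or PR". Secondary efficacy endpoints in this cohort are also analysed as randomized.

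**The concern.** In a randomized cohort analysed as randomized, the conditions that decide whether a subject belongs in the population should be settled before randomization. Here the condition that defines the disease carries a deadline at a later milestone. The adjacent item shows that the authors could tie a requirement to randomization when they meant to.

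A site that follows 2.c.i literally could randomize a subject with a radiologic diagnosis while the pathology report is pending. If the report does not show HCC, the subject cannot start therapy, has no on-treatment response to record, and stays in the denominator as a non-responder. The result is a randomized but untreatable subject in an open-label cohort, and an ORR slightly diluted by a subject outside the target disease. Both are avoidable, because the tissue must already be at the central vendor.

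**Working it through.** **Step 1. Deadline against denominator.**

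| Cohort | Latest time stated for histology | ORR denominator | Do they match? |
|---|---|---|---|
| Expansion (3.3.1.1, 2.b) | before study therapy starts | all treated | yes |
| 1L (3.3.2.1, 2.c.i) | before study therapy starts | all randomized | no |
| Combination (3.3.3.1, 2.b.i) | before study therapy starts | all treated | yes |

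The wording suits the cohorts whose ORR is based on treated subjects. In the 1L cohort the denominator is fixed one step before the deadline.

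**Step 2. Does another rule close the gap?** The tissue requirement concerns receipt and quality, and neither 2.c.ii nor Table 5.1-2 says that the check establishes HCC. The screening window is counted from first dose, so being in screening does not by itself mean before randomization. Section 3.3 makes the criteria conditions of entry into the study without equating entry with randomization. Taken together, these passages suggest that histology should be in hand by the end of screening, but no sentence in the 1L text available for this review says so for histology.

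**Step 3. Reproduce the plan's figures.** Synopsis Table 1 uses n = 65 per arm. The exact 95% limits are: lower = Beta quantile(0.025; x, n − x + 1); upper = Beta quantile(0.975; x + 1, n − x).

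- x = 13: 13/65 = 20.0%, limits 11.1% and 31.8%, as in Table 1.
- x = 10: 10/65 = 15.4%, limits 7.6% and 26.5%, as in Table 1.
- x = 3: 3/65 = 4.6%, limits 1.0% and 12.9%, as in Table 1.
- x = 2: 2/65 = 3.1%, limits 0.4% and 10.7%, as in Table 1.

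The 90% lower bounds in Table 1 also reproduce, as one-sided exact bounds.

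**Step 4. Size of the dilution.** The documents give no rate of failed histology after randomization. Assume that k of 65 subjects in an arm turn out not to have HCC, are never treated, and count as non-responders. The ORR among HCC subjects is then x/(65 − k), and the understatement is x/(65 − k) − x/65 = (x/65) × k/(65 − k).

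| k | 13 responders | Exact 95% CI | Shift (points) | 10 responders | 3 responders |
|---|---|---|---|---|---|
| 0 | 13/65 = 20.0% | 11.1% to 31.8% | – | 15.4% | 4.6% |
| 1 | 13/64 = 20.3% | 11.3% to 32.2% | 0.3 | 15.6% | 4.7% |
| 3 | 13/62 = 21.0% | 11.7% to 33.2% | 1.0 | 16.1% | 4.8% |
| 5 | 13/60 = 21.7% | 12.1% to 34.2% | 1.7 | 16.7% | 5.0% |

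For k = 5 and x = 13: 0.200 × 5/60 = 0.0167, or 1.7 points. The 95% interval at 13/65 is 31.8 − 11.1 = 20.7 points wide.

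**The case against.** The strongest reply is that the protocol, read as a whole, does not permit what 2.c.i seems to allow. Histology is inclusion criterion 2.c itself. The concession for radiologic diagnosis covers enrolment for screening only, criteria are assessed in screening, no exceptions are granted, and there is a re-enrolment route for screen failures. On that reading, randomizing without histology would be an eligibility breach. This largely stands. A reader might infer that the protocol knowingly lets subjects without HCC be randomized, and the documents do not support that. What remains is that the one sentence giving histology a deadline names the wrong milestone for this cohort.

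It is also fair to say that the shift is small, that it lowers the ORR rather than inflating it, and that the cohort now estimates ORR in each arm without a formal comparison, so no error rate is affected.

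Four further inferences are tempting and should not be drawn:

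- *That the tissue check should rule out fibrolamellar, sarcomatoid or mixed tumors.* Section 3.3.2.2 excludes these only when known.
- *That the limit "Within 14 days prior to first dose" on the physical examination and ECG leaves eligibility open after randomization.* It is a recency limit within a screening table, and the ascites exclusion is judged at screening.
- *That the loss would differ by arm.* The tissue is submitted before assignment, so what it shows cannot depend on the arm, and no text seen allows exclusion after randomization.
- *That Stage 1 of the combination cohort would fall short of 12 per arm.* The documents give no figure to support this, and ORR there is based on treated subjects.

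**Conclusion.** The point holds as a minor one: a mis-set deadline in a single criterion. The text does not clearly intend randomization without histology, but its literal deadline and a screening window anchored to first dose allow it, and the primary denominator would then retain the subject.

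Under the assumed 1 to 5 affected subjects of 65 per arm, an observed 20.0% understates the ORR among HCC subjects by 0.3 to 1.7 points, and an observed 4.6% does so by 0.1 to 0.4 points. Neither would change how the estimate is read, given the width of the intervals. The range of k is an assumption, as is the premise that affected subjects are never treated and never recorded as responders.

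The text available for this review ends at the start of Table 5.1-3. Sections 8.2 and 8.4, on populations and analyses, could not be checked for a rule on randomized but ineligible subjects.

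**What to change.** In Section 3.3.2.1 item 2.c.i, change the deadline from the start of study therapy to *prior to randomization*. In Table 5.1-2, extend the row on inclusion and exclusion criteria with the Table 5.1-1 instruction that they be confirmed before randomization.

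The same phrase may be changed in Section 3.3.3.1 item 2.b.i for consistency, although the denominator problem does not arise in that cohort.

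The cost is one phrase in one criterion (two if the combination cohort is aligned) and one line in a table. No new procedure is needed, since tissue is already required before randomization. The only downside is that a few subjects with a radiologic diagnosis wait for a pathology report before they can be randomized.
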